5. STUDY ASSESSMENT AND PROCEDURES

This will be a collaborative study between Washington State University, Pillsy, Inc, and the clinical site Ideal Option (opioid and other substance use disorders treatment center). The overarching goal is to evaluate if the use of the Pillsy system will improve treatment adherence. The study coordinator will work closely with the medical assistant from the clinical site, conducting a scripted screening, by phone or in person, documenting substance use, addiction treatment history, medical and psychiatric history, medications and availability of social support. Only patients recently initiating BUP/NAL treatment will be approached to assess their eligibility for the study.

The clinical site will be responsible for the BUP/NAL prescription and treatment plan. Participants will receive their prescription medications through their normal pharmacy. Pillsy, though the RC will provide the Pillsy system which includes the smart bottle cap (Pillsy Cap), the mobile application (Pillsy App), and the SMS texting platform with a brief training on how to utilize the system. Pillsy Cap tracks when the bottle is opened or closed. Figure 1 (below) is a draft CONSORT diagram of participant flow through the study protocol.

[figure not shown]

Figure 1. Overview of study Procedures and CONSORT Diagram for Participant Flow.

Intervention

Participants will be directed to preferably bring their pill bottle and medication in for their baseline visits. While it is possible for us to orient participants to the intervention before they have received their prescription or after even if they don't have the bottle, this lessens the training experience substantially and could decrease the utility of the cap and efficacy of the system. The RC will orient the participants in the use of the Pillsy app. The participants in both groups will also have full access to the services normally provided by the prescribing office including blood testing and counseling services. The Pillsy intervention consists of a Smart Pill Cap and a mobile phone application. All participants will receive the Pillsy cap (to track pill bottle openings), but only the active group will receive the Pillsy app with messaging and reminders. Please note this when reading the below, since the below is what the PLY group will receive, but not the SAU group.

If the patient does not take their medicine at the correct time, a light on the smart pill cap begins to flash. If the bottle is not opened within 20 minutes, the Pillsy application sends an SMS text reminder to the patient's phone. If the bottle is not opened within 60 minutes, the patient receives an automated phone call. The patient may also receive brief motivational phrases that can be tailored to patient needs and preferences. Pillsy also includes a "Pillsy Helpers" feature in which the patient can name friends and family members who will also receive a text message notification one hour after a missed dose. Thus, if the patient is struggling, his or her support system can attempt to contact the patient and offer motivation. Importantly, as proposed in the clinical trials detailed in this application, the MAT prescriber can also be a Pillsy Helper.

All data handling will conform to meet HIPAA requirements, including administrative, physical, and technical safeguards. Data will be encrypted in storage and in rest in REDCap with regularly scheduled data deposits from Pillsy into REDCap.

Participants in the service as usual (SAU) arm will receive a prescription for BUP/NAL tablets/sublingual films and any services normally provided by the prescribing office. Participants in the SAU arm will receive an "inactive" Pillsy smart cap that will track openings but will not provide reminders or any other messaging.

Screening Visit

The RC will screen the patient to assess the participant's appropriateness for the study. If the prospective participant meets inclusion/exclusion criteria, the RC will explain the clinical study in detail and informed consent will be obtained. If eligible, the participant will be trained on how to use the Pillsy system (cap and app) if randomized to PLY group. No training will be needed for the SAU. While their cap will be activated to capture open and close times, that is the only data that will be collected on the cap. and randomized to one of the study groups.

Week 1 Assessment

Study participants will return to office as frequently as the prescriber sees fit in the course of addiction treatment. At 1 week +/- 1 day, the RC will count BUP/NAL tablets/sublingual films and compare to the prescribed number of pills for that period. Participants will complete questionnaires.

Week 6 Assessment

Study participants will return to office as frequently as the prescriber sees fit in the course of addiction treatment. At 6 weeks +/- 2 days, the RC will count BUP/NAL tablets/sublingual films and compare to the prescribed number of pills for that period. Participants will complete questionnaires.

Week 12 Assessment

Study participants will return to office as frequently as the prescriber sees fit in the course of addiction treatment. At 12 weeks +/- 3 days, or RC will count BUP/NAL tablets/sublingual films

and compare to the prescribed number of pills for that period. Participants will complete questionnaires.

Ongoing Assessments

Pillsy will continuously collect data on pill bottle openings, missed doses, text messages sent, automated phone calls made, etc. If there is a loss of contact, or the participant stops their engagement with the study, the RC will attempt to contact the participant (up to two (2) attempts) with an exit interview, by phone. If no answer, no message will be left. The coordinator will attempt to call again 2-3 business days later for a final attempt to describe reasons for withdrawal from the study.

Table 1. Schedule and Types of Assessments Performed: MAP4BUP Phase I.

	Screening/Baseline	Week 1	Week 6	Week 12
Informed consent	X			
Verify inclusion/exclusion criteria are met	X			
AUDIT	X			
Demographics	X			
Fagerström	X			
Addiction Severity Index – Lite	X			
Timeline Follow-Back of medication use and drug and alcohol use	X	X	X	X
DSM-5 OUD Checklist*	X			
Pill/film count and self-report of prescriptions	X	X	X	X
Barratt Impulsiveness Scale (BIS) 8	X	X	X	X
Opioid Craving Scale	X	X	X	X
Healthy Days Core Module (CDC HRQOL-4)	X	X	X	X
Sleep Related Impairment	X	X	X	X
Sleep Disturbance	X	X	X	X
Pain Intensity	X	X	X	X
Pain Interference	X	X	X	X
Standard counseling, prescribing, dose changes**	As needed, determined by prescribing provider and medical team.			
Pillsy System Usability Questionnaire		X		X
Adverse event monitoring	X	X	X	X
Reason for quitting	Administered once, triggered by predefined non-adherence to the treatment.			

*Diagnostic and Statistical Manual of Mental Disorders, Fifth Edition (DSM-5) Opioid Use Disorder (OUD) research checklist

**To be guided by the discretion and standard practices of the prescriber.

Laboratory Assessment

Ideal Option performs comprehensive histories and physical examinations as well as collecting samples for required laboratory tests. Ideal Option has private bathrooms and locations that are commonly used for collection of urine samples. Ideal Option collects and processes urine

samples as part of their day-to-day operations. Through a signed data use agreement, all of this data will be made available to Washington State University for combination with research data at the end of the study.

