1. PROTOCOL SUMMARY

1.1 SYNOPSIS

Title: Mobile Medication Adherence Platform for Buprenorphine-Naloxone (MAP4BUP) During Treatment of Opioid Use Disorder: Phase I MAP4BUP Study

Opioid misuse and abuse affect the health and the well-being of millions of Americans. On average, 130 Americans die every day from an opioid overdose in 2017, according to CDC data. Opioid agonist therapy, such as buprenorphine-naloxone (BUP/NAL), can reduce opioid overdose deaths, decrease opioid misuse, and improve quality of life. Unfortunately, poor medication adherence is a barrier to long term efficacy of this therapy. To assess compliance, we plan to substantially monitor adherence to inexpensive oral buprenorphine-naloxone with Pillsy, a Bluetooth-connected smart pill cap and pharmacy software platform. The technology platform was developed over the past three years using principles of behavioral science, modern design, and highly scalable wireless and mobile technologies.

We will build out and adapt our current Pillsy platform, then test it in a small-scale trial to assess feasibility, usability, and effectiveness. We propose, in Phase I, to conduct a study involving 30 subjects selected randomly among patients prescribed (BUP/NAL) for opioid misuse to better understand their willingness to use Pillsy and identify areas of problematic compliance. Using the data obtained in Phase I and after meeting with the FDA, we will further refine the platform in Phase II. This will be a collaborative study between Washington State University, Pillsy and the clinical site Ideal Option.

The purpose of this randomized, controlled trial in Phase I is to determine whether the Pillsy intervention can improve adherence to BUP/NAL compared to services as usual (SAU). The primary endpoint will be adherence to MAT as determined through the medication possession ratio at the end of the trial. The hypothesis is that the Pillsy intervention will significantly improve adherence to medication-assisted treatment (MAT) compared with SAU.

Study Design

Narrative Study Description

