The research coordinator (RC) will provide the Pillsy device and orient the participants in the use of the Pillsy app. Participants in both groups will also have full access to services normally provided by the prescribing office including blood testing and counseling services (i.e. SAU). All participants will receive the Pillsy cap (to track and time stamp pill bottle openings, closings, etc). The participants assigned to the Pillsy intervention, will also have a mobile phone reminder application. If the participant does not take their medicine at the correct time, a light on the smart pill cap will flash. If the bottle is not opened within 20 minutes, the Pillsy app sends an SMS text message to participant's phone. If the bottle is not opened within 60 minutes, the participant then receives an automated phone call. The participant may also receive brief motivational phrases or craving surveys that can be tailored to participant needs and preferences.

Pillsy also includes a Pillsy Helpers feature in which the participant can name friends and family members who will also receive a text message notification one hour after a missed dose. If the participant is struggling, his or her social support can attempt to contact the participant. The MAT prescriber may also be a Pillsy Helper. The MAT prescriber may be contacted when the participant has missed a dose if they are designated as a helper, giving the prescriber the opportunity to intervene. Providers may decide to call the imminently nonadherent participant to provide a brief, timely therapeutic intervention for which the provider can bill using the 99091 CPT code.

All data handling will conform to appropriate regulatory guidelines (HIPAA) and will be collected in such a way that it can be integrated into existing EMRs. The long-term goal is for this information to be available to one's prescriber and provider in real-time for monitoring.

Participants in SAU arm will receive a prescription for BUP/NAL tablets/sublingual films and any services normally provided by the prescribing office. Participants in SAU arm will receive an inactive Pillsy smart cap that will track openings but will not provide reminders or any other messaging.

Primary Endpoint

Adherence to BUP/NAL treatment assessed by medication possession ratio (pills taken/pills prescribed)

Secondary Endpoints

1. Participant engagement quantified through office visits and assessed via real time surveys

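### The primary adherence ratio needs the number of pills taken, but the plan neither defines that number nor records what was dispensed, so the pill count cannot tell unfilled supply from supply taken

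*Combined protocol and SAP*

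**What the plan says.** The Synopsis (1.1) gives the primary endpoint as "Adherence to BUP/NAL treatment assessed by medication possession ratio (pills taken/pills prescribed" and places the comparison at the end of the trial: "adherence to MAT as determined through the medication possession ratio at the end of the trial".

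Section 5 describes one procedure for obtaining it, in near-identical words at weeks 1, 6 and 12: "the RC will count BUP/NAL tablets/sublingual films and compare to the prescribed number of pills for that period". Table 1 lists the corresponding item as "Pill/film count and self-report of prescriptions" and schedules it at Screening/Baseline as well as at those three visits.

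On supply, Section 5 says "Participants will receive their prescription medications through their normal pharmacy", and on prescribing, "The clinical site will be responsible for the BUP/NAL prescription and treatment plan". Section 4.4 notes that patients may already have been given up to 30 days of medication before the referral visit. The Intervention text says "Participants will be directed to preferably bring their pill bottle and medication in for their baseline visits".

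Two other data sources bear on whether doses were taken. Cap openings are recorded in both arms, and Table 1 schedules a Timeline Follow-Back that covers medication use at every visit. The document does not say that either enters the primary ratio.

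**The concern.** A count at a visit shows what is left. To turn it into what was taken, one must know what the participant had available: the stock at the previous count plus whatever was dispensed since. The plan secures the prescribed number and the remaining number, but not the dispensed number. It also leaves the step from those two numbers to the numerator unwritten.

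An empty bottle at week 6 or 12 can therefore mean that everything prescribed was filled and taken, or that part of it was never collected. The ratio gives both the same value. If the two arms differ in how reliably prescriptions are filled, that part of the adherence difference is lost or distorted in the primary comparison. Section 6.1 says the trial is meant to show some improvement in adherence and to inform Phase II, so a ratio that cannot see one route of non-adherence weakens its main output.

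**Working it through.** The plan states no figure on this point, so there is none to reproduce. The check follows the described procedure through to a score.

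**Notation.** P = units prescribed for the period, D = units dispensed, T = units taken, L = units left at the count, S = stock at the previous count (zero unless stated).

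- True ratio, from the endpoint definition: T/P.
- Score from the count and the prescribed number alone: (P − L)/P. This is inferred, because the formula is not written.
- Score if the unfilled prescription is not reported, so the denominator shrinks to D: (D − L)/D.
- Score with a dispensing record: (S + D − L)/P.

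The unit numbers and fill shares below are assumptions; the document gives none.

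**Individual cases, P = 84**

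| Case | D | T | L | True T/P | (P − L)/P | (D − L)/D | (S + D − L)/P |
|---|---|---|---|---|---|---|---|
| All filled, 8 left | 84 | 76 | 8 | 0.905 | 0.905 | 0.905 | 0.905 |
| Half filled, all of it taken | 42 | 42 | 0 | 0.50 | 1.00 | 1.00 | 0.50 |
| One third unfilled, 80% of the rest taken | 56 | 44.8 | 11.2 | 0.533 | 0.867 | 0.80 | 0.533 |
| Nothing filled | 0 | 0 | 0 | 0 | 1.00 | undefined | 0 |

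The participant who collected half the supply scores above the one who collected all of it and left 8 units. Shrinking the denominator does not penalise non-filling either.

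**Arm level.** Assume 30% of supply unfilled under SAU and 10% under Pillsy, with 90% of filled units taken in both arms.

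- True: 0.9 × 0.7 = 0.63 and 0.9 × 0.9 = 0.81, a difference of +0.18.
- Scored as (P − L)/P: 1 − 0.1 × 0.7 = 0.93 and 1 − 0.1 × 0.9 = 0.91, a difference of −0.02.
- Scored as (D − L)/D: 0.90 and 0.90, a difference of 0.

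With equal fill shares in the two arms (20% each) and the same 90% taken, the true and scored differences are both 0. The distortion of the comparison in this example comes from unequal filling.

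**Supply already held.** Suppose 2 units a day, 30 days in hand (60 units), no new fill by week 1, full adherence, and no opening count. Then 14 units are prescribed for the week and 60 − 14 = 46 are left. Prescribed minus remaining gives 14 − 46 = −32. With the opening stock known, S + D − L = 60 + 0 − 46 = 14, and the ratio is 14/14 = 1.00. Uncounted stock thus pushes the score in the opposite direction from non-filling.

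**The case against.** Several points on the other side are sound and limit what can be claimed.

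- **The subtraction is not in the protocol.** The text says only that the count is compared with the number prescribed. A reader might infer that the plan lays down a rule scoring unfilled supply as taken. It does not; it lays down no rule. But no rule applied to those two numbers can separate unfilled from taken supply.
- **Other data could expose an empty bottle.** Cap openings and the Timeline Follow-Back are collected and could show that no doses were being taken. This stands as a means of cross-checking, but neither is assigned to the ratio, and self-reported adherence is a separate secondary endpoint.
- **A baseline count is planned.** Table 1 schedules it, so opening stock is not ignored. The gap is that bringing the bottle is a preference, and there is no instruction for when it is not brought.
- **Self-report may not be the denominator.** Table 1 does not say so, and the clinic writes the prescriptions. But clinic records are not named as the source and would not show what was dispensed. The linked data, of which the protocol says "Through a signed data use agreement, all of this data will be made available to Washington State University", are described there as histories, examinations and laboratory samples.
- **Participants who leave may miss the count.** They would then be missing data under Section 6.4, not scored as fully adherent. The error applies to those who attend after not filling or part-filling.
- **This is a 30-person proof of concept.** That lowers the severity, but not the need for a numerator that can be computed.

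**Conclusion.** The point holds: the numerator of the primary endpoint has no written derivation, and the quantity needed to derive it is not collected. A participant who attends with unfilled or part-filled prescriptions would be scored too high on the natural reading. On the alternative reading the unfilled prescription leaves the ratio unpenalised. In the half-filled illustration the score is 1.00 against a true 0.50.

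The effect on the arm comparison cannot be estimated from the document, which gives no fill rates. Three stronger conclusions are not supported:

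- **That the bias must run towards no difference.** This would require Pillsy to improve filling, which the document does not assert. The assumed example above even reverses the sign.
- **That failing to refill is a main route of non-adherence here.** Section 2.1 reports poor retention, which is a different thing.
- **That the loss can be expressed as a share of the 20% improvement in Section 6.1.** That figure is a Phase II planning effect translated to an odds ratio of 2.4, and is not comparable with a difference in mean ratio.

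This should be fixed before enrolment, because analysts may be unable to reconstruct fills that nobody recorded.

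**What to change.** In the week 1, 6 and 12 assessment text of Section 5, and in Table 1:

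1. Define pills taken as stock at the previous count, plus quantity dispensed since then, minus stock remaining, and state that unfilled quantity counts as not taken.
2. At each visit, record in REDCap the date and quantity of every fill since the last one, from pharmacy labels or a fill printout.
3. Take pills prescribed from the clinic's prescribing record rather than from self-report, after confirming that the data use agreement covers it.
4. Obtain the baseline count for everyone. If the bottle is not brought, record opening stock from the last fill label or by report, and flag it. Keep the measurement window starting at randomisation in both arms; starting it at the first recorded fill would discard early non-filling.
5. Prespecify cap openings as a cross-check on the count.

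The cost is protocol wording, one REDCap form, an extract of prescriptions, and a few minutes more per visit. Some fill records will be incomplete, since counts can be six weeks apart and the current label may not show interim fills. The average ratio will be lower than under prescribed minus remaining wherever supply goes unfilled.

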2. INTRODUCTION

2.1 STUDY RATIONALE

The United States is in the midst of an opioid epidemic. According to the Substance Abuse and Mental Health Services Administration (SAMHSA) 2016 estimates, 11.5 million people misuse their prescription opioids, 948,000 use heroin, and 2.1 million people meet diagnostic criteria for opioid use disorder (OUD). A documented 42,249 Americans died of opioid overdose in 2016, which is an average of 116 preventable deaths per day ¹. Opioid Agonist Therapy (OAT), such as buprenorphine/naloxone (BUP/NAL), can reduce opioid overdose deaths by at least 70%, decrease opioid misuse, and improve quality of life. Because of its proven efficacy, the National Institute on Drug Abuse (NIDA), the Substance Abuse and Mental Health Services Administration (SAMHSA), the American Society of Addiction Medicine (ASAM), and the American Academy of Addiction Psychiatry (AAAP) endorse the use of medication-assisted therapy in the treatment of OUD.

Poor medication adherence is one of the main barriers to long term efficacy of opioid agonist therapy (OAT). A year-long outpatient study of OAT in 225 treatment-seeking patients with opioid use disorder (OUD)² showed that treatment retention fell to under 50% by 12 weeks and only 25% of patients remained at one year. Novel depot formulations of efficacious drugs can improve adherence. However, in Ling's study, depot opioid agonists provided only a modest increase in adherence (13.8% compared to oral buprenorphine/naloxone BUP/NAL) despite the significant (565%) price increase compared to the generic drug.

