6. STATISTICAL CONSIDERATIONS

6.1 Sample Size

For this Phase I study we are planning to randomize 15% of the targeted N (200) of a full-scale Phase II study, resulting in a total of 30 subjects, 15 per arm. More than anything, this is designed as a “proof-of-concept” study to demonstrate that Pillsy can produce some amount of adherence improvement and is both feasible and useful to patients so we can plan a larger version of this study in Phase II.

Sample size calculations – Our choice of sample size for the Phase II trial (n=200) was based on power calculations for detecting a 20% increase in our primary outcome of increasing adherence to BUP/NAL while also considering treatment retention assessed by office visits and assuming a 25% attrition rate in our cohort. This translates to an OR of 2.4, which we would have 99% power to find based on 3 longitudinal assessments and assuming we are examining the between effect only. Using a more conservative estimate of a 10% change, we would still have 90% power to detect this effect (OR of 1.6).

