6.4 Handling of Missing data

If data are missing, the absence of data will be handled in a manner consistent with current expert recommendations, some of which have been established by our own team.³⁻⁶ Our approach emphasizes either maximum likelihood or multiple imputation. All participants who dropped out will be included in all analyses up to the time of withdrawal.

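### The exit contact specifies no adherence item, so adherence after the last coordinator count is not captured for the primary ratio in participants who leave

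*Combined protocol and SAP*

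**What the plan says.** The synopsis defines the primary endpoint as "adherence to MAT as determined through the medication possession ratio at the end of the trial", with the ratio being pills taken over pills prescribed. Section 5 describes how units are counted: at weeks 1, 6 and 12, "the RC will count BUP/NAL tablets/sublingual films and compare to the prescribed number of pills for that period". Table 1 adds a baseline count.

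For participants who drop out of contact or stop engaging, section 5 (Ongoing Assessments) says "the RC will attempt to contact the participant (up to two (2) attempts) with an exit interview, by phone". No message is left if there is no answer, and the second call is described as follows: "The coordinator will attempt to call again 2-3 business days later for a final attempt to describe reasons for withdrawal from the study". The matching row of Table 1 is a reason-for-quitting form, given once when a preset level of non-adherence is reached. Section 5.1.3 adds that coordinators will seek discontinued participants' views of the Pillsy intervention.

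On analysis, section 6.2 names generalized estimating equations as an example of the repeated-measures methods. Section 6.4 keeps dropouts in the analyses as far as their withdrawal and says "Our approach emphasizes either maximum likelihood or multiple imputation".

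**The concern.** The study already plans to phone people who stop engaging, but the stated purpose of the call is why they left. Units left and doses taken since the last count are not listed, although Table 1 already has instruments for both: the pill/film count and the Timeline Follow-Back of medication use.

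This matters because leaving is plausibly related to the outcome, and Table 1 itself makes non-adherence the trigger for the quitting form. Maximum likelihood and multiple imputation, in their usual form, assume that people who leave resemble those who stay with the same observed history. They cannot see a fall in adherence that begins after the last count unless some later information enters the model. No analysis allowing for such a fall is named. With 15 people per arm and results meant to inform Phase II, a few unobserved people can move the estimate that is carried forward.

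**Working it through.** **Step 1. Where adherence is measured and what is asked at exit.**

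- Scheduled counts: baseline and weeks 1, 6 and 12 (Table 1, section 5).
- Exit contact: reasons for withdrawal (section 5), reason for quitting (Table 1), views of the intervention (section 5.1.3). No adherence item is specified.
- Other adherence data: caps record openings in both arms throughout (section 5). The documents do not say that openings may stand in for a missing count in the ratio.

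**Step 2. How much follow-up is uncounted.** If the last count is at week 6, up to 12 − 6 = 6 of 12 weeks have no count. If it is at week 1, up to 12 − 1 = 11 of 12 weeks have none.

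**Step 3. How many people.** The planned size reproduces: 0.15 × 200 = 30. No Phase I attrition rate is given, so two benchmarks from the protocol are used.

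- Section 6.1, for Phase II, "assuming a 25% attrition rate in our cohort": 30 × 0.25 = 7.5, so 7 or 8 people without a week 12 count.
- Section 2.1, from a cited outpatient study, "treatment retention fell to under 50% by 12 weeks": 30 × 0.50 = 15, so more than 15 people. That figure is retention in treatment elsewhere, not missing study counts here, so it is a loose upper benchmark.

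**Step 4. Completers-only illustration.** Let d be the share lost, r the mean ratio in those retained and m the true mean ratio in those lost. The documents give neither r nor m, so both are assumed.

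True arm mean = (1 − d) × r + d × m. Overstatement if only completers are used = d × (r − m).

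| r | m | d | True mean | Overstatement |
|---|---|---|---|---|
| 0.85 | 0.40 | 25% | 0.7375 | 0.1125 |
| 0.85 | 0.40 | 50% | 0.625 | 0.225 |
| 0.85 | 0.75 | 25% | 0.825 | 0.025 |
| 0.85 | 0.75 | 50% | 0.80 | 0.05 |

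**Step 5. Difference between arms.** If r and m are the same in both arms and only the loss differs, completers show a difference of 0. The all-randomised difference is (loss in SAU − loss in PLY) × (r − m).

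- Assumed loss 50% v 30%, r = 0.85: 0.20 × 0.45 = 0.09 if m = 0.40; 0.20 × 0.10 = 0.02 if m = 0.75.
- Assumed loss 6/15 v 2/15, r = 0.90: (4/15) × (0.90 − m) = 0.24, 0.16 or 0.08 for m = 0, 0.3 or 0.6.

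With equal loss in the two arms the hidden difference in this model is 0.

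**Step 6. What these figures leave out.** They ignore the week 1 and week 6 counts, which the planned analysis would use. They show how the result depends on m, which is the quantity the exit contact does not ask about. They do not estimate the bias of the planned analysis.

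**The case against.** The strongest case on the other side has five parts.

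- *The exit calls may ask more than is written.* A reader might infer that they ask only why the person left. The documents do not contain the interview script, so they support no more than that no adherence item is specified. This stands.
- *The primary outcome is not lost.* A reader might infer that it is. Counts before withdrawal are kept, caps record openings in both arms with regular transfers to REDCap, and clinic data come under a data use agreement. This largely stands. But openings are not units, they depend on continued use of the cap, and they are not designated as a source for the ratio. The clinic data are described as histories, examinations and laboratory results, with no unit count.
- *The illustration is not the planned analysis.* A reader might infer that a real 9-point advantage would show as zero. That result follows from giving both arms the same ratio within retained and lost participants and using completers only. The plan is a longitudinal model with maximum likelihood or multiple imputation. This stands.
- *An exit call cannot recover the week 12 value.* It reaches only to the date of the call, and only those who answer. This stands and limits what the change can achieve.
- *Phone self-report is weaker than a coordinator count,* and self-reported adherence is already a secondary endpoint. This stands as a reason not to place such values directly in the primary analysis.

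**Conclusion.** The point holds as a gap in data collection and in the stated data sources. The plan specifies no adherence item at exit and no rule on whether cap openings may replace a missing count. Adherence after the last count is therefore not captured for the primary ratio in people who leave. That their leaving is tied to non-adherence is a reasonable inference supported by the trigger in Table 1, not an established fact.

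The outcome is only partly lost, and the size of any bias under the planned analysis cannot be derived from the documents. The completers-only overstatement at 25% loss runs from 2.5 to 11 points for assumed ratios of 0.75 to 0.40 in those lost. It would be nil if those lost were as adherent as those retained. The change is worth making because it is cheap and bears on the primary endpoint, even in a 30-person proof-of-concept study.

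**What to change.** In section 5, Ongoing Assessments, add two items to the existing exit call for participants who have not withdrawn consent to data collection: the number of BUP/NAL units remaining, and the medication part of the Timeline Follow-Back since the last count. Record both flagged by source.

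In section 6.4, state:

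- whether cap openings may stand in for a missing count;
- that exit-call values and cap openings enter the imputation or likelihood model as auxiliary information;
- that a sensitivity analysis of the primary ratio, specified in advance, uses them;
- that one further analysis assumes lower adherence after contact is lost, over a stated range.

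The cost is a few more minutes on calls already planned, plus the extra analyses. Phone reports are weaker than a coordinator count, and they cover only the time up to the call and only those who answer, so missing data will remain.
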